6.3. Other Eligibility Criteria Considerations

To assess any potential impact on subject eligibility with regard to safety, the investigator must refer to the Nelotanserin Investigator's Brochure for detailed information regarding warnings, precautions, contraindications, AEs, and other significant data pertaining to the investigational product being used in this study:

6.4. Screening Failures

Screen failures are defined as subjects who sign an informed consent form (ICF) for the study but do not enter the single-blind placebo run-in period. A minimal set of screen failure information is required including demography, disease history, screen failure details, eligibility criteria, and any AEs.

Subjects who are screen failures may be rescreened, only after approval by the study medical monitor.

6.5. Withdrawal Criteria

6.5.1. Reasons for Withdrawal

A withdrawal from the study is defined as withdrawing any time after entering the single-blind placebo run-in period and before completion of the EOS visit (Visit 5). Subjects who permanently discontinue use of investigational product will be considered to be withdrawn from the study. Subjects may withdraw from the study at any time and for any reason. The investigator (or designee) must document the reason for withdrawal in the Study Conclusion section of the case report form (CRF). Information related to AEs will continue to be collected as per usual procedures on subjects who have discontinued investigational product. Withdrawn subjects during double-blind period will not be replaced. The reasons for subject withdrawal will be recorded and may include, but are not limited to:

- Any clinical AE, laboratory abnormality, or other medical condition or situation occurs such that continued participation in the study would not be in the best interest of the subject in the opinion of the investigator
- Significant protocol violation
- Subject requests to discontinue for any reason; it is important to determine whether the withdrawal of consent is primarily due to an AE, lack of effectiveness, or other reason
- Subjects don't meet the eligibility criteria at baseline (Visit 4)

The above reasons do not automatically lead to withdrawal from the study in all cases. The final decision will be based on consultation between the principal investigator and the study medical monitor, with the ultimate decision by the principal investigator or subject.

If a subject requires initiation of obstructive sleep apnea/central sleep apnea (OSA/CSA) treatment based on Visit 3 sleep laboratory assessments, the subject will be considered a run-in failure. After stable treatment and satisfactory adherence to treatment established for at least 2 weeks (eg, continuous positive airway pressure [CPAP] >4 hours usage nightly for at least 70% of nights or evidence of effective treatment based on patient/caregiver report), the run-in failed subject may be considered for participating in this study for the second and final time. The subject will be re-consented and assigned a new study ID.

If a subject discontinues during the placebo run-in period, the Early Termination Visit sleep laboratory assessment will not be required, but all other early termination procedures must be performed. If a subject meets discontinuation criteria during double-blind treatment, an Early Termination Visit (including sleep laboratory) will be required.

Subjects who meet any of the following laboratory abnormality criteria will be discontinued from the study (adapted from FDA Draft 2009 Guidance for Industry Drug-Induced Liver Injury: Premarketing Clinical Evaluation):

- ALT or AST >5xULN, confirmed by immediate repeat testing
- ALT or AST >3xULN and TBL >2xULN or INR >1.5, confirmed by immediate repeat testing
- ALT or AST >3xULN, confirmed by immediate repeat testing, with a concurrent report of fatigue, nausea, vomiting, right upper quadrant pain or tenderness, fever, rash, and/or eosinophilia (>5%). If, upon repeat testing of liver chemistry, the symptoms outlined have resolved, but the liver chemistry still meet the noted criteria, subjects should discontinue study treatment.

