17. Subjects with a history of Gilbert's Syndrome, Dubin-Johnson Syndrome, Rotor Syndrome, Familial Intrahepatic Cholestasis, Gaucher's disease, or other inherited metabolic diseases that have the potential to effect hepatic function should be discussed with the medical monitor;
18. Subjects with aspartate transaminase (AST), alanine transaminase (ALT), or serum total bilirubin level (TBL) test values greater than the upper limit of the laboratory reference (normal) range (ULN);
19. Subjects with prothrombin time (PT)/international normalized ratio (INR) greater than the ULN, – subjects receiving warfarin or coumadin and an INR <3 may be allowed to participate if approved by the medical monitor;

20. Subjects who have a clinically significant abnormality in other clinical laboratory results or other clinical conditions that, in the opinion of the investigator/medical monitor, would prevent the subject from safely participating in this study.

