12. If a subject discontinues due to run-in failure, the Early Termination sleep laboratory will not be required. If a subject meets discontinuation criteria during double-blind treatment, an Early Termination Visit (including sleep laboratory) will be required.
13. All subjects who are taking dopaminergic drugs (eg, levodopa, dopamine agonist) should ideally be assessed for UPDRS during their "on" state (if applicable). Record the name, dose and time of last administration of the dopaminergic drug, the subject's on/off state (if applicable), and the time of the UPDRS assessment. The timing of UPDRS assessment from last administration of dopaminergic drug should remain consistent across the study for a given subject.
14. C-SSRS Screening/Baseline version will be used at Visit 1, and C-SSRS Since Last Visit version will be used at Visit 5/ET.
15. Fasting serum samples will be collected for bile acids analysis. A minimum of 8 hours fasting is required. If the patient is unable to meet the fasting requirement, sample for the bile acids testing should not be drawn; this should be documented in the patient's records as well as the appropriate case report form. Samples will be stored and bile acid analysis may be performed if there is a liver specific safety signal or as part of a retrospective analysis.
16. Only ALT, AST, alkaline phosphatase, total and direct bilirubin will be included for chemistry samples collected at this visit, along with PT, INR and fasted bile acids. Laboratory samples will be taken by a visiting phlebotomist at subject's residence. The subject can make an unscheduled visit to the site or a local lab to have the lab samples drawn.
17. Subjects randomized to nelotanserin 80 mg/matching placebo will receive two (2) 20-mg nelotanserin/matching placebo tablets for 5 days before the dose is titrated to four (4) 20-mg nelotanserin/matching placebo tablets for the remainder of the double-blind period. A phone call should be made approximately 6 days after randomization visit to confirm up-titration occurred. Date and time of first dose taken for 80mg nelotanserin/placebo will be recorded.
18. VAS is optional if a bed partner is not available. A bed partner is defined as the person who sleeps in the same bedroom as the subject.

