8.3.2.1.9. Regulatory Reporting Requirements for Serious Adverse Events

Prompt notification by the investigator to the sponsor or sponsor representative of all SAEs and nonserious AEs occurring during a clinical trial is essential so that legal obligations and ethical responsibilities towards the safety of subjects and the safety of a product under clinical investigation are met.

All Hy's law cases will be reported as SAEs. A Hy's law case is defined as ALT or AST >3xULN and TBL >2xULN, alkaline phosphatase <2xULN.

The Sponsor has a legal responsibility to notify both the local regulatory authority and other regulatory agencies about the safety of a product under clinical investigation. The Sponsor will comply with country specific regulatory requirements relating to safety reporting to the regulatory authority, Institutional Review Board (IRB)/Independent Ethics Committee (IEC) and investigators.

IND safety reports are prepared for suspected unexpected serious adverse reactions (SUSAR) according to local regulatory requirements and the Sponsor policy and are forwarded to investigators as required by the regulations.

An investigator who receives an investigator safety letter describing an SAE(s) or other specific safety information (eg, summary or listing of SAEs) from the Sponsor will be kept in the investigator's regulatory binder with the Investigator's Brochure and will notify the IRB/IEC, if appropriate according to local requirements.

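### The second liver discontinuation criterion leaves its and/or terms ungrouped and uses an absolute INR cut-off that subjects admitted under the warfarin exception may already exceed

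*Combined protocol and SAP*

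**What the plan says.** Section 6.5.1 (Reasons for Withdrawal) introduces three laboratory criteria with a mandatory clause: "Subjects who meet any of the following laboratory abnormality criteria will be discontinued from the study". The second criterion is "ALT or AST >3xULN and TBL >2xULN or INR >1.5, confirmed by immediate repeat testing". The first requires ALT or AST above 5xULN. The third requires ALT or AST above 3xULN together with listed symptoms or eosinophilia.

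Section 6.2.2 sets the entry limits. Exclusion 18 rules out "Subjects with aspartate transaminase (AST), alanine transaminase (ALT), or serum total bilirubin level (TBL) test values greater than the upper limit of the" laboratory range. Exclusion 19 rules out PT/INR above the upper limit, with an exception: "subjects receiving warfarin or coumadin and an INR <3 may be allowed to participate if approved by the medical monitor". The Protocol Summary repeats the exception.

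INR is measured again after entry. Table 2 in Section 8.1 schedules it at Visit 4 and at the final or early termination assessments. The table's note on the Day 14 sample lists the liver chemistry "along with PT, INR and fasted bile acids".

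No section exempts anticoagulated subjects from the INR term, ties it to a baseline value, or otherwise says how it applies to them.

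**The concern.** The protocol knowingly admits some subjects whose INR is raised by an anticoagulant, then uses a fixed INR threshold below the admission limit in a mandatory liver stopping rule. It does not say how the two fit together. The missing grouping adds a second uncertainty, because whether the INR term can act alone or only alongside raised ALT/AST depends on how a site reads the sentence.

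Two things are at stake. A subject could be stopped for a laboratory value that reflects the anticoagulant and not the liver, and would then appear among the discontinuations as an apparent liver case. Section 6.5.1 also counts permanent discontinuation of investigational product as withdrawal from the study, and subjects withdrawn in the double-blind period are not replaced. A needless stop can therefore affect when, or whether, the primary endpoint is measured.

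**Working it through.** The plan states no figure to reproduce. The check treats the criterion as a logical rule and applies it to the values the protocol allows.

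**Inputs**
- T: ALT or AST above 3xULN; B: TBL above 2xULN; I: INR above 1.5 (Section 6.5.1).
- At entry ALT, AST and TBL are at most 1xULN (exclusion 18), so T and B are both false.
- At entry under the warfarin exception INR is strictly below 3 (exclusion 19), so I is true whenever 1.5 < INR < 3.

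**Two readings**
- Reading 1: (T and B) or I.
- Reading 2: T and (B or I), which expands to (T and B) or (T and I).

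**Results for this criterion alone**

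| Situation | ALT/AST (xULN) | TBL (xULN) | INR | Reading 1 | Reading 2 |
|---|---|---|---|---|---|
| Entry | 1 | 1 | 1.0 or 1.5 | not met | not met |
| Entry, warfarin | 1 | 1 | 1.6, 2.0, 2.5 or 2.99 | met | not met |
| On treatment, warfarin | 2 | 1 | 2.5 | met | not met |
| On treatment, warfarin | 3.1 | 1 | 2.5 | met | met |
| On treatment | 3.1 | 1 | 1.0 | not met | not met |
| On treatment | 3.1 | 2.1 | 1.0 | met | met |

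**How the readings relate.** If T is true, both readings reduce to (B or I) and agree. If T is false, Reading 2 is never met and Reading 1 reduces to I. The readings therefore differ only when INR exceeds 1.5 without ALT/AST above 3xULN. Every case that meets Reading 2 also meets Reading 1, so Reading 1 can only add discontinuations.

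**What Reading 2 leaves unresolved.** Rows 4 and 5 of the table have the same ALT/AST and TBL and differ only in INR, yet only the first meets the criterion. Taking all three criteria together, the gap is bounded. ALT/AST above 5xULN stops either subject under the first criterion, and listed symptoms or eosinophilia with ALT/AST above 3xULN stop either subject under the third. The two are treated differently when ALT/AST is above 3 and at most 5xULN, TBL is at most 2xULN, and none of the third criterion's findings is present.

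**Whether another provision removes the problem**
- Repeat testing: an INR raised by continuing anticoagulation would be expected to be raised again on repeat.
- Discretion: the sentence "The above reasons do not automatically lead to withdrawal from the study in all cases" refers to the list of reasons before it. The laboratory criteria come later, under their own mandatory clause.
- Waivers: Section 8 allows none except for immediate safety concerns.
- Medical monitor approval: it governs entry and does not say how the stopping criterion applies afterwards.

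**Scale.** One DLB subject is 1/34 = 0.029, about 3% of the planned primary sample (Section 10.2). The number of anticoagulated subjects is not given, so no total can be computed.

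**The case against.** The strongest reply is that Reading 2 is plainly meant. The INR term stands inside a criterion that opens with ALT/AST, the other two criteria both need raised ALT/AST, and Section 6.5.2 describes follow-up for subjects stopped because of liver test elevations. Reading 1 would also defeat much of the exception in exclusion 19. As an argument about textual coherence this is persuasive, and it makes Reading 2 the more likely intent. The sentence still does not say so, and Reading 2 leaves the INR part satisfied by the anticoagulant.

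A reader might infer three stronger things that the documents do not support.

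- *Sites could reach contrary decisions, with one reading missing a stop that the other requires in each direction.* The readings are nested. Reading 1 contains Reading 2, so the dispute is only about extra discontinuations.
- *The entry exception and the stopping rule flatly contradict each other.* That holds only under Reading 1. Under Reading 2, exclusion 18 keeps ALT/AST low enough that the criterion cannot be met on the entry values.
- *Each needless stop loses a primary endpoint.* Sections 6.5.1 and 8.1 require an Early Termination visit with sleep laboratory assessment for subjects stopped in double-blind treatment. The Full Analysis Set needs a post-baseline primary assessment, not completed treatment (Section 10.3.1). Section 10.4 adds a multiple-imputation sensitivity analysis for missing end-of-study values. What remains is that the recording may fall before the planned 28 days of treatment, or be missed. No sleep laboratory visit is required for a subject stopped during the run-in.

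It is also fair to say that the exception needs approval case by case, so the medical monitor will know which subjects are concerned.

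**Conclusion.** The point holds as a gap between two parts of the protocol that must be reconciled. For subjects admitted with 1.5 < INR < 3, the second criterion is met with normal liver tests under one reading. Under the more plausible reading, ALT/AST above 3xULN alone is enough to meet it. Neither consequence is stated or adapted anywhere in the protocol.

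The direction of the risk is over-discontinuation and a false liver signal, not a missed stop. Its size is unknown because the count of anticoagulated subjects is not given. The figure of about 3% describes one hypothetical DLB subject whose endpoint is actually missed, and the required Early Termination recording makes that outcome possible but not automatic.

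The conclusion assumes that the anticoagulant keeps INR above 1.5 during the study and that sites follow the mandatory wording as written. It makes no judgement on which INR threshold or grouping is clinically right.

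**What to change.** Reconcile exclusion 19 (Section 6.2.2 and the Protocol Summary) with the second laboratory criterion in Section 6.5.1:

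1. Write the criterion so that the grouping of the ALT/AST, TBL and INR terms is explicit.
2. State how the INR condition applies to subjects admitted under the warfarin exception.

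The clinical content of both is for the sponsor's medical team. The cost is a clarifying sentence or two in Section 6.5.1 by amendment. No change is needed to the sample size, the assessment schedule or the efficacy analysis.

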6.5.2. Subject Withdrawal Procedures

If a subject is prematurely discontinued from treatment with the investigational product, the investigator must make every effort to perform the evaluations scheduled for the Early Termination Visit (Table 2). In the case where the subject permanently discontinues study medication between scheduled clinic visits he/she should be recalled to the clinic as soon as possible and preferably within 7 days of stopping study medication for the Early Termination Visit; it is important to record the date and time of the last study dose.

All subjects discontinuing due to liver function tests (LFTs) elevation will be followed frequently with additional laboratory testing (1-2 times weekly) until all laboratory abnormalities return to normal or to the baseline state. The medical monitor(s) should be notified of all cases with serum aminotransferase $>3xULN$ or TBL $>2xULN$ immediately after it is first reported. Other liver safety tests (eg, viral hepatitis panel, autoimmune hepatitis tests, tests for cytomegalovirus [CMV] and Epstein–Barr virus [EBV], blood draw for pharmacokinetic [PK] analysis) will be collected at confirmatory laboratory, and additional tests and examinations may be requested at the medical monitor's discretion.

Lost to follow-up: If a subject is lost to follow-up, every effort must be made by study center personnel to contact the subject, inquire about the reason for discontinuation/withdrawal, and follow up with any unresolved AEs/serious adverse events (SAEs). A minimum of 3 attempts at contact should be made with 1 contact being by certified letter. All measures taken to contact the subject and information received during those attempts must be documented.

7. STUDY TREATMENT

7.1. Investigational Product and Other Study Treatment

Nelotanserin 20-mg tablets and matching placebo tablets are composed of an immediate-release, blue, oblong shaped tablet containing common pharmaceutical excipients in a compacted powder blend. The excipients used for the proposed clinical program are commonly available, generally regarded as safe, and tested against appropriate compendial acceptance criteria. The tablets are coated with a cosmetic colored film-coat. Lactose monohydrate is the only excipient used in the manufacture of RVT-102 (nelotanserin) tablets that is animal-sourced. The vendor source of this excipient has certified that ingredients used in the manufacture of lactose monohydrate are Bovine spongiform encephalopathy/transmissible spongiform encephalopathy free.

7.2. Randomization/Treatment Assignment

During the screening and the single-blind placebo run-in period, subjects will be identified by their initials, screening number (3 digits), and date of birth. Subjects who meet all screening eligibility criteria at Visit 2 will receive single-blind placebo (2 x placebo tablets) for up to 30 days during the single-blind placebo run-in period. The tablet will be administered once-daily in the evening, at approximately 1 hour before bedtime. The subject will be instructed to take the study drug around the same time each day. If subjects continue to meet all eligibility criteria, they will be randomized and assigned a randomization identification number (4 digits). Both screening and randomization numbers will be used to identify the subject on any related study documents. The Investigator will keep a record relating the names of the subjects to their identification numbers, to allow easy checking of data in subject files, when required. A central randomization process based on an Interactive Voice/Web Response System (IXRS) will be utilized. The investigative sites will be provided a 4-digit (eg, 1001) randomization number. The randomization number will be entered on the CRFs for each subject.

Eligible subjects will be randomized (1:1) to either the nelotanserin 80-mg treatment group or the placebo group during the double-blind period. The randomization will be stratified by disease type (DLB or PDD) and by whether the subjects will continue to take clonazepam (or other benzodiazepines) or melatonin concurrently with the study treatment.

The study medications used in the trial are nelotanserin 20 mg and matching placebo tablets. Subjects randomized to nelotanserin 80 mg will receive two (2) 20-mg nelotanserin tablets (40 mg/day) for 5 days before the dose is titrated to four (4) 20-mg nelotanserin tablets (80 mg/day) for the remainder of the double-blind period. In order to mask the treatment assignment, subjects randomized to placebo will similarly receive 2 placebo tablets for 5 days and then 4 matching placebo tablets for the remainder of the double-blind period. A phone call should be made approximately 6 days after randomization visit (V4) to confirm up-titration occurred. Date and time of first dose taken for 80-mg nelotanserin/placebo will be recorded.

7.3. Blinding

The 20 mg nelotanserin and matching placebo tablets will be identical in appearance.

7.4. Packaging and Labeling

Study medications are provided in high-density polyethylene bottles with child-resistant caps. The bottles contain 30 tablets and should be stored at room temperature (59°F-77°F; 15°C-25°C).

Protect from light.

The study tablets will be ingested orally without food (at least 1 hour before or 2 hours after a meal) at approximately 1 hour before bedtime.

The label for the investigational product will contain at a minimum the following information:

- Protocol number
- Lot number
- Quantity
- Dosing directions
- “Caution: New Drug – Limited by Federal law to investigational use. Keep out of reach of children.”

7.5. Preparation/Handling/Storage/Accountability

The Investigator, pharmacist, or other appropriate individual who is designated by the Investigator, is responsible for correct storage of the study medication according to the manufacturer's recommendations. The study medication made available for this clinical trial must be used in accordance with the protocol, under the responsibility of the Investigator. The Investigator or other appropriate individual who is designated by the Investigator must maintain complete and accurate records, showing the receipt and disposition of all supplies of the study medication delivered by the Sponsor. These records must include date of receipt of all drug shipments, all batch numbers, and the quantities received. In addition, records of medication dispensed must be maintained, detailing the quantity dispensed, identification of the person to whom study medication was dispensed, the date of each dispensing, and the identification of the dispenser.

